### 5.5.2 Missed Dose

Dosing visits should be scheduled at intervals of 4 weeks from Visit 3A, with a window of  $\pm 2$  days. In the event that a visit needs to be rescheduled it may be rearranged such that it falls no later than 7 days before or after the original 4 week interval from the prior dose. On successful completion of a rearranged dosing visit the next dose should then be scheduled as per the original schedule ( $\pm 2$  days).

If it is not possible to reschedule within 3-5 weeks of the previous dose then it should be considered a missed dose and the next dose should be scheduled in accordance with the original schedule (± 2 days) provided that this does not result in an interval between any two doses of less than 3 or greater than 5 weeks.

## 5.6 Blinding

This is a double-blind study and the active treatments and placebo are identical in appearance both before and after reconstitution and administration. During the conduct of the study, the subject, Investigator/study staff, Circassia Ltd and the Clinical Research Organisation (CRO) staff directly involved in the clinical study will remain blind to the treatment group. Wherever possible, and considering the best interests of the study subject, once study medication has been administered, management of any subsequent AE should not be predicated upon knowledge of a subject's treatment assignment.

Where the Investigator believes that unblinding is required, they should document and explain the reasons for any unblinding of the study (e.g., due to a Serious Adverse Event (SAE)). The Investigator may discuss the decision to unblind with the Sponsor's medical monitor should time permit.

### 5.7 Randomisation

Subjects who successfully complete Period 1 Screening and continue to meet the study entry criteria at the end of the BAE, will be randomised to receive placebo or one of the HDM-SPIRE regimens. The Randomisation Schedule will be produced by a computer-generated algorithm by HMD Clinical.

Subjects will be randomised on an equal basis (i.e. 1:1:1:1) to placebo and each of the 3 HDM-SPIRE treatment groups.

VERSION FINAL 4.0 CONFIDENTIAL PAGE 35 OF 92

Randomisation will be stratified according to the following criteria:

DATE 01 APRIL 2015

- Current history of asthma (present or absent)
- Mean TRSS during BAE ( $<16, \ge 16$ )

Study medication packs will be assembled in accordance with the Randomisation Schedule. An interactive response technology (IRT) system will be used to allocate study medication packs to subjects, according to the randomisation and stratification schema. The Investigator or designee will also record the Subject Screening Number against the allocated randomised study pack on the Drug Accountability Record.

## **5.8** Concomitant Medication and Dietary Supplements

### 5.8.1 Rescue Medication

Subjects may, at any time during the study, take allergy medication. During the BAE and PAC periods subjects will be asked to use only allergy rescue medication provided to the subject in the Rescue Medication Package according to the defined Rescue Medication Plan (Appendix 3).

The following allergy rescue medications will be provided to subjects and their use will be documented in their eDiaries during the BAE and PAC periods:

- Antihistamine eye drops
- Oral antihistamines
- Intranasal corticosteroids

If a subject finds that he or she is not able to obtain a comfortable level of relief from symptoms with the allergy rescue medications provided during the BAE, the Investigator and subject may agree to use alternative allergy rescue medications in the same categories as above. Alternative allergy rescue medications will be scored on the same RMS scale as the equivalent category of allergy rescue medication from the Rescue Medication Package. The Investigator may also prescribe oral corticosteroids, if required and their use will be documented in the subjects' eDiaries during the PAC periods.

A subject who uses any other category of allergy medications than those included in the Rescue Medication Package during the BAE Period will not be randomised. Use of any other category of allergy medications during the PAC periods will be considered a protocol deviation.

VERSION FINAL 4.0 CONFIDENTIAL PAGE 36 OF 92

Subjects will be instructed to record all allergy medications other than those provided in the Rescue Medication Package in the pDiary.

The recorded allergy rescue medication usage data in the eDiary will be transferred into the study database directly. No duplication of recording in eCRF is required.

All allergy rescue medications dispensed or prescribed to subjects as part of the Rescue Medication Package will be recorded in the eCRFs.

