#### 6.2.1.2.1 Visit 2A

The following procedures will take place at Visit 2A:

- Each subject will be provided with an eDiary to record RSS, Asthma Symptom Scores (ASS) and allergy rescue medication use.
- Recording of any changes to concomitant medication since last visit.
- Recording of any AEs.
- Dispense a pDiary to record AEs and concomitant medications.
- Subjects will be requested to discontinue their current allergy medication. Subjects will be trained on how to follow the study-specific Rescue Medication (Appendix 3) and will be asked to only use medications from the Rescue Medication Package for the duration of the BAE.
- Dispense allergy rescue medication.

The following information will be recorded in the eDiary on a daily basis first thing in the morning for a period of 3 weeks:

- RSS on a 4 point categorical scale
- Allergy rescue medication use
- ASS

If a subject's allergic rhinoconjunctivitis symptoms become unacceptable to them, they may take allergy rescue medications from the Rescue Medication Package provided in accordance with the Rescue Medication Plan (Appendix 3). Subjects will be instructed to inform the Investigator if they have taken any allergy medication other than those prescribed from the Rescue Medication Package. The Investigator must record these allergy medications as concomitant medications in the eCRF.

For each symptom, the subject will rate the severity over the last 24 hours as follows:

- 0 = absent
- 1 = mild, barely noticeable
- 2 = moderate, annoying/troublesome
- 3 = severe, very annoying/ very troublesome

**RSS symptoms** will be captured as follows:

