#### **Non nasal Symptoms**

- Itchy eyes
- Watery eyes

- Red eyes
- Itchy ear/palate

The use of **rhinoconjunctivitis rescue medications** will be scored based on Didier et al (Didier 2009) as follows:

- RMS = 0; no rescue medication used per day;
- RMS = 0.5; at least one dose of antihistamine eye drops used per day;
- RMS = 1; at least one dose of oral antihistamine used per day;
- RMS = 2; at least one dose of intranasal corticosteroid used per day;
- RMS = 3; at least one dose of systemic corticosteroid used per day.

Where a subject finds that he or she is not able to obtain a suitable level of relief from symptoms with the provided allergy rescue medications, the Investigator and subject should discuss the use of alternative allergy rescue medications in the same categories as above. Alternative allergy rescue medications will be scored on the same RMS scale as the equivalent category of allergy rescue medication from the Rescue Medication Package.

Asthma Symptom Scores (ASS) will be captured as follows for all subjects using the same 4 point (0-3) grading scale described above:

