## 7.5.3 Efficacy Analysis

## 7.5.3.1 Primary Analysis

#### 7.5.3.1.1 Combined Score (TRSS and RMS)

The primary endpoint for this study is the mean daily CS during the PAC3 period in HDM-SPIRE treated subjects compared with mean daily CS during the PAC3 period in placebo treated subjects. The CS is a composite measurement of symptoms as measured by the TRSS and RMS, as measured using a pre-defined rating system that takes into account the different potency of available rescue medication.

The TRSS comprises assessment of 8 symptoms (4 nasal and 4 non-nasal symptoms) that are given a score of between 0 (absent) and 3 (severe) giving a range of potential scores of 0 to 24. Subjects are asked to record the average intensity of their symptoms over the last 24 hours once each morning for 3 weeks in the baseline and PAC periods.

Subjects also record their use of any of the provided rescue medications in the previous 24 hours. These are assigned a score as follows:

- RMS = 0; no allergy rescue medication used per day
- RMS = 0.5; at least one dose of antihistamine eye drops used per day
- RMS = 1; at least one dose of oral antihistamine used per day
- RMS = 2; at least one dose of intranasal corticosteroid used per day
- RMS = 3; at least one dose of systemic corticosteroid used per day

The RMS score is not additive, and therefore the maximum RMS is 3.

The TRSS (0-24) and the RMS (0-3) will be combined for analysis of the primary endpoint as follows:

CS = TRSS/8 + RMS

The maximum Combined Score is therefore 6.

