## 15. EFFICACY OUTCOMES

### 15.1. PRIMARY EFFICACY

#### 15.1.1. PRIMARY EFFICACY VARIABLE & DERIVATION

The primary efficacy analysis is to be performed for the ITT population and repeated for the PP population.

The primary efficacy variable is the mean of the daily combined score (CS) during the PAC3 period as recorded on each subject's eDiary.

The daily total rhinoconjunctivitis symptom score (TRSS) and the daily rescue medication score (RMS) are to be combined and a daily CS is to be calculated for each subject as follows:

- $CS = (TRSS / 8) + RMS$

For each subject the mean of the daily non-missing CS during the BAE, PAC1, PAC2 and PAC3 periods is to be calculated as follows:

- $\text{Sum(All CS in respective period)} / \text{Number of non-missing days in respective period}$

The TRSS is the sum of 8 individual TRSS symptom scores, namely runny nose, sneezing, blocked nose, itchy nose, itchy eyes, watery eyes, red eyes and itchy ear/palate. All symptoms are reflective over the previous 24 hours.

For each symptom, the subject is to rate (each morning) the severity as follows:

0 = absent

1 = mild, barely noticeable

2 = moderate, annoying/troublesome

3 = severe, very annoying/very troublesome

The TRSS is to have a range of 0 to 24. The TRSS on each day is to be calculated as follows:

TRSS = Runny Nose + Sneezing + Blocked Nose + Itchy Nose + Itchy Eyes + Watery Eyes + Red Eyes + Itchy Ear/Palate.

Rescue medications are to be provided to subjects to be used according to a pre-specified Rescue Medication Plan as specified in protocol Appendix 3: Rescue Medication Package Description and Rescue Medication Plan. The use of allergy rescue medications is to be scored based on Didier (Didier *et al*, 2009) as follows:

- RMS = 0; no allergy rescue medication used per day
- RMS = 0.5; at least one dose of antihistamine eye drops used per day
- RMS = 1; at least one dose of oral antihistamine used per day
- RMS = 2; at least one dose of intranasal corticosteroid used per day

---

Document: TH005 SAP Version 2.docx

Author: [name]

Version Number:

2.0

Version Date:

24MAR2017

Template No: CS\_TP\_BS016 – Revision 3

Effective Date: 01May2012

Reference: CS\_WI\_BS005

Copyright © 2012 Quintiles Transnational Corp. All rights reserved.

The contents of this document are confidential and proprietary to Quintiles Transnational Corp. Unauthorized use, disclosure or reproduction is strictly prohibited.

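### Same-category allergy medicines from outside the Rescue Medication Package must count in RMS but are routed to the pDiary, so a day on them alone can score RMS = 0

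*Protocol*

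**What the plan says.** **Scoring.** Protocol 5.8.1 allows a subject without adequate relief to agree on a different product in the same drug classes, and gives the rule: "Alternative allergy rescue medications will be scored on the same RMS scale as the equivalent category of allergy rescue medication". Protocol 6.2.1.2.1 (Visit 2A) repeats this: "the Investigator and subject should discuss the use of alternative allergy rescue medications in the same categories as above", again with scoring by equivalent class.

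**Recording.** For the Package medicines, 5.8.1 says: "The following allergy rescue medications will be provided to subjects and their use will be documented in their eDiaries during the BAE and PAC periods". For everything else it says: "Subjects will be instructed to record all allergy medications other than those provided in the Rescue Medication Package in the pDiary". Protocol 6.2.1.2.1 adds, for allergy medicines not from the Package: "The Investigator must record these allergy medications as concomitant medications in the eCRF". The Visit 2B and end-of-PAC procedures (6.2.1.2.2, 6.2.3.1) likewise expect some allergy medication to be absent from the eDiary and collect it with the concomitant medications.

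**Source of the score.** Protocol 7.5.3.1.1 describes the RMS input this way: "Subjects also record their use of any of the provided rescue medications in the previous 24 hours". Protocol 8.4.1 names the eDiary as the source of RMS for the efficacy analyses. SAP 3.1 takes each period's RMS from the scores entered in the eDiary. SAP 15.1.1 defines the primary variable as "the mean of the daily combined score (CS) during the PAC3 period as recorded on each" subject's eDiary.

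**Other use of the eCRF records.** SAP 12 and 15.3.1.4 use allergy medication on the concomitant-medication eCRF for summaries and a used/not-used comparison. Neither section links it to daily RMS.

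**The concern.** One section gives two instructions that cannot both take effect. The medicine is to be scored, but it is recorded where the score does not look.

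The missing-data rules do not catch this. A subject who takes only an alternative product and writes it in the pDiary as told can have a complete eDiary day with no rescue medication entered. That day enters mean CS with RMS = 0. Under SAP 15.2.1.5 it can also count as a well day if no symptom scores above 1. Any relief from the medicine still shows in TRSS, so both halves of CS look better on a day when more medication was used. The BAE mean CS, which is the model covariate, is built the same way.

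What is at stake is the PAC3 treatment difference. Unscored days that are more common on placebo shrink it. Unscored days that are more common on active treatment inflate it.

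**Working it through.** **1. Data flow for a day on which only a same-category, non-Package medicine is taken**

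- Must it be scored? Yes, by class: 0.5 (antihistamine eye drops), 1 (oral antihistamine) or 2 (intranasal corticosteroid) (Protocol 5.8.1, 6.2.1.2.1).
- Where is it recorded? In the pDiary and then the concomitant-medication eCRF (Protocol 5.8.1, 6.2.1.2.1, 7.1).
- Where does RMS come from? The eDiary (Protocol 8.4.1; SAP 3.1, 15.1.1).
- Does any step link the two? I found none in either document.
- Result: RMS can be 0 instead of 0.5, 1 or 2.

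If a Package medicine is also entered that day, RMS takes that medicine's category, because the daily score is a maximum (SAP 15.1.1). The loss is then smaller or nil. Oral corticosteroids are also outside the Package (Protocol Appendix 3), but 5.8.1 expressly assigns them to the eDiary in the PAC periods, so the gap concerns the other three classes.

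**2. The plan's design figure** (Protocol 7.2: difference 0.32, SD 0.986, two-sided 0.05, 80% power)

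n per group = 2 × (1.960 + 0.842)² × 0.986² / 0.32² = 149.1, rounded up to 150. This reproduces the plan.

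SE = 0.986 × √(2/150) = 0.1139, and power = Φ(0.32/0.1139 − 1.960) = 80.3%.

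**3. Effect on one subject** (nominal 21-day period, complete diary, no Package medicine entered on the affected days)

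Loss in mean CS = points × affected days / 21. For 7 days:

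- eye drops: 0.5 × 7/21 = 0.17
- oral antihistamine: 1 × 7/21 = 0.33
- intranasal corticosteroid: 2 × 7/21 = 0.67

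**4. Effect on the group difference**

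Shift = excess share of unscored subject-days in one arm × points per day. The documents give no frequencies, so the excesses below are assumptions. The remaining difference and power take the excess to be on placebo, with 150 per group and SD 0.986 unchanged.

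| Points per day | Excess | Shift | Remaining difference | Power |
|---|---|---|---|---|
| 0.5 | 2% | 0.01 | 0.31 | 77.7% |
| 0.5 | 5% | 0.025 | 0.295 | 73.6% |
| 1 | 2% | 0.02 | 0.30 | 75.0% |
| 1 | 5% | 0.05 | 0.27 | 66.0% |
| 2 | 2% | 0.04 | 0.28 | 69.1% |
| 2 | 5% | 0.10 | 0.22 | 48.9% |

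In the nasal-steroid rows the shift is 0.04/0.32 = 12.5% and 0.10/0.32 = 31% of the target. An excess on active treatment would inflate the difference by the same amounts. Equal use gives no average shift.

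**The case against.** The best defence is that RMS is defined by drug class and not by who supplied the product. A day on an alternative antihistamine does not meet the definition of RMS = 0, and the daily eDiary item is described generally as allergy rescue medication use (Protocol 6.2.1.2.1, 6.3.1). The pDiary sentence follows a paragraph on other categories of medication and could be meant for those only. The eDiary already takes one non-Package class, oral corticosteroids. The screens and subject training are not in the documents. This reading is possible, so it would be wrong to infer that every day on an alternative scores 0. But no passage tells subjects to enter alternatives in the eDiary, and the pDiary sentence taken literally tells them to record these elsewhere. That 5.8.1 names the eDiary for oral corticosteroids makes its silence on alternatives more telling.

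A second defence is that exposure is narrow. In 5.8.1 the switch arises from poor relief in the BAE, before randomisation, so who switches should be balanced on average. In the PAC periods subjects are asked to keep to the Package and are retrained on the plan. This stands as a limit on size. It does not rule out unequal use in PAC3.

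A third is that the SAP already compares concomitant allergy medication by arm and repeats the primary analysis in the PP population. Those outputs may reveal unequal use but do not correct the score. SAP 12 also removes rescue-plan medicines from its definition of concomitant medication, and Appendix 3 lists that plan by class, so a same-class alternative might drop out of the comparison too.

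**Conclusion.** The concern holds as a defect in the written scoring rule. Followed literally, the plan can record a complete day with RMS = 0 when a scorable medicine was taken. The loss is 0.5, 1 or 2 CS points on that day, or less if a Package medicine is also entered. PAC means, baseline CS and well days are all exposed.

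The effect on the treatment difference cannot be estimated from the documents. A reader might infer from the table that the primary result is biased by up to 31% of the target, or that it is biased towards placebo. Neither is supported: the 2 and 5 percentage-point excesses have no source, the 0.10 figure takes the highest-scoring of the three affected classes with no Package medicine entered, and the direction is unknown. The table shows only that a modest imbalance would matter on a target of 0.32, which is enough to justify settling the rule before unblinding.

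**What to change.** Reconcile the passages in Protocol 5.8.1, 6.2.1.2.1 and 7.5.3.1.1 by stating that same-category non-Package medicines are entered in the eDiary under their class. If the eDiary already worked this way, documenting that in the SAP closes the point.

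For data already collected without that instruction, add to SAP 15.1.1:

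- a mapping of non-Package allergy medicines to RMS categories, made blind at the blind data review;
- daily RMS as the maximum of the eDiary category and the mapped category, on days where dated pDiary or eCRF records show use;
- the same derivation for BAE, PAC1, PAC2 and PAC3, carried through to well days.

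Do not spread as-needed, partial-date or missing-stop-date records over every day between start and stop. SAP Appendix 2 treats a completely missing stop date as ongoing, and Protocol 5.8.4 includes as-needed medication, so filling by date range could put 1 or 2 points on days without use. Handle those days in a sensitivity analysis, for example scored by class in one run and with CS set to missing in another. Treat days on out-of-category allergy medication in the same analysis.

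The cost is a small amount of blinded mapping and one derivation step. Some date uncertainty will remain, because no passage shows that day-by-day use is captured in the eCRF. Treatment is unchanged.

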## 5.8.2 Treatment of Suspected Anaphylactic Reactions

Anaphylactic reactions may be life-threatening and any suspected anaphylactic reaction must be treated immediately.

All medications and medical equipment for the treatment of suspected anaphylactic reactions must be immediately available at the study centre.

Appendix 2 presents an example of algorithms for the management of suspected anaphylactic reactions (Resuscitation Council United Kingdom [UK], 2008 and Anaphylaxis Emergency Action Plan). The Investigator may follow their own national guidelines or Standard Operating Procedure (SOP) for treating suspected anaphylactic reactions, but a copy of the Guideline or SOP must be placed in the Investigator Site File and have been verified to be suitable by the CRO managing the study.

For all but the mildest cases of anaphylaxis, subjects should be hospitalised overnight or monitored for at least 12 hours.

All cases of anaphylaxis or suspected anaphylaxis must be recorded as an **AE of Special Interest** and should be reported in an expedited manner to the Sponsor in the same way as an SAE (See Section 6.4.2.1). The report must include a grading of the event using the World Allergy Organization Subcutaneous Immunotherapy Systemic Reaction Grading System (See Appendix 4).

#### 5.8.3 Asthma Medication

Subjects with asthma should be controlled and compliant with Treatment Step 1 or Step 2 (see GINA, Appendix 1). Treatment for asthma must have been stable (drug(s), dose, frequency) for at least 3 months prior to screening.

Short acting bronchodilator should not be used for a minimum of 4 hours before each spirometry assessment.

VERSION FINAL 4.0 CONFIDENTIAL PAGE 37 OF 92

Full details of the subject's asthma medications will be entered into the eCRF. Use of short-acting inhaled  $\beta_2$  agonist and inhaled corticosteroid medications during the BAE Period and each PAC period will be recorded in the eDiary.

#### 5.8.4 Other Medication

The Investigator should record the use of all concomitant medications, both prescribed and over-the-counter, into the eCRF and subject's medical records. This includes medications used on both a chronic and an as-needed basis. Subjects should be discouraged from starting any new medication, both prescribed and over-the-counter, without consulting the Investigator, unless the new medication is required for emergency use.

Hormonal contraceptives may be used by FOCBP. The peptides used in treatment are designed to induce immunological tolerance via binding to major histocompatibility complex Class II on antigen-presenting cells and are therefore not anticipated to interact with hormonal contraceptives.

#### 5.8.5 Contraindicated Medication, Devices and Dietary Supplements

The following medications are not permitted during Periods 1 and 2 of the study. A minimum washout period of 14 days is required before Screening visit 1B/C.

- beta-blockers
- alpha-adrenoceptor blockers
- monoamine oxidase inhibitors

Subjects using any of the above during Period 1 will not be randomised and during Period 2 will be withdrawn from the study.

Subjects are prohibited from starting any other form of immunotherapy during the study.

## 6.0 STUDY CONDUCT

#### 6.1 **Schedule of Assessments**

The study procedures, efficacy and safety assessments will be made as shown in **Table 5**.

